A total of sixty (60) subjects scheduled to undergo salpingo-oophorectomy within 30 days of BR55 CEUS examination will be enrolled to obtain approximately 30 subjects with benign ovarian lesions and 30 with malignant ovarian lesions based on the TS.

BR55 will be evaluated in the study as follows:

The first 10 subjects enrolled in the study will receive BR55 at a dose of 0.03 mL/kg. Assuming these first 10 subjects will show technically adequate images, subsequent subjects enrolled in the

study will continue to receive 0.03 mL/kg dose of BR55; otherwise, subjects will be switched to a 0.05 mL/kg dose of BR55.

The final cancer diagnosis will be obtained for all subjects by histopathology.

Study Duration

A subject's participation will begin at the time of signing the informed consent through the 24 hour follow-up after the administration of BR55.

The procedure planned, namely the ovarian ultrasound examination with administration of BR55, will be completed within 60 minutes including up to 30 minutes of CEUS examination.

Safety monitoring will begin at the time of signing the Informed Consent and will continue for 24 hours after BR55 administration.

Study Population

It is planned to enroll a maximum of 60 female subjects scheduled to undergo salpingo-oophorectomy for suspected ovarian cancer within 30 days of the BR55 CEUS examination, but not before completion of the safety assessment at 24 hours post BR55 administration.

Inclusion Criteria

Enroll a subject in this study if the subject meets the following inclusion criteria:

- Is at least 18 years of age;
- Has an ovarian lesion that is visible and assessable with trans-vaginal ultrasound;
- Is scheduled to undergo salpingo-oophorectomy for suspected ovarian cancer not earlier than 24 hours and not later than 30 days following BR55 administration;
- Provides written Informed Consent and is willing to comply with protocol requirements.

Exclusion Criteria

Exclude a subject from this study if the subject does not fulfill the inclusion criteria, or if any of the following conditions are observed:

- Is a pregnant or lactating female. Exclude the possibility of pregnancy:
 - by testing on site at the institution (serum Beta Human Chorionic Gonadotropin, β HCG) within 24 hours prior to the start of investigational product (IP) administration,
 - by surgical history (e.g., tubal ligation or hysterectomy),
 - by post-menopausal status with a minimum 1 year without menses;

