A standardized UEUS, as used in clinical imaging, will be conducted in all subjects to ensure a comprehensive survey of pelvic structures and organs and to identify the target ovarian lesion (as defined in the imaging manual). In case of complex cystic ovarian lesions, the target lesion is defined as the solid component of the lesion itself. Optimally, it should be possible to view the entire lesion within the field of view of the ultrasound probe. UEUS will also serve to identify the optimal plane for imaging the target lesion after BR55 administration.

After BR55 administration, the contrast inflow into the target lesion will be observed on the optimal imaging plane for approximately 45 seconds using a low frame rate to minimize

destruction of targeted bubbles. Subsequently, post-contrast images will be acquired at predefined time intervals (outlined in the dedicated imaging manual) up to 30 minutes post BR55 administration or until stationary enhancement in the lesion is still no longer visible, whichever occurs first.

DICOM images will be transferred to the Bracco Imaging Core Laboratory.

Efficacy Evaluations

Visual Assessment of BR55 Enhancement

BR55 contrast-enhanced images will be assessed by the investigator using the following semi quantitative scale:

1. No enhancement: No focal targeted, stationary imaging signal is detectable
2. Weak enhancement: Weak focal targeted imaging signal is detectable and considered as possibly stationary
3. Strong enhancement: Well defined and strong focal targeted imaging signal is detectable and considered as definitely.

Quantitative Assessment of BR55 Enhancement

A quantitative assessment of contrast enhancement with BR55 will be performed by drawing a Region of Interest (ROI) within the target lesion to measure SI.

Pathology and immunohistochemistry measurements for Ovary lesions

Histopathology measurements and immunohistochemistry analysis will be described in a separate dedicated manual.

Statistical Methods

Analysis Population

Safety analysis population will consist of all subjects who are dosed.

Efficacy analysis population will include the data from all subjects who are dosed and have efficacy data available.

Extent of Exposure

Descriptive statistics will be presented to summarise the volume of investigational medicinal product (IMP) administered. Dosing of the BR55 will be listed.

Safety Analysis

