Characterization of BR55 CEUS in Ovary Cancer

| BR55 CEUS | Truth Standard | | |
|-----------|--------------------|--------------------|-------------------|
| | Negative | Positive | Total |
| Negative | TN | FN | N _{CEUS} |
| Positive | FP | TP* | P _{CEUS} |
| Total | N _{truth} | P _{truth} | TOTAL |

TP = True Positive; TN = True Negative; FP = False Positive; FN = False Negative.
* TP is exact match of malignant lesion between BR55 CEUS and TS.

$$Sensitivity = \frac{TP}{TP + FN}, \quad Specificity = \frac{TN}{TN + FP}, \quad Accuracy = \frac{TP + TN}{TP + FN + TN + FP},$$

B55 CEUS Differentiates between Malignant and Benign Ovarian Lesions - Ultrasound Signal Intensity (SI) vs. TS

The purpose of the analyses is to explore the threshold of SI (quantitative assessment of BR55 enhancement) on BR55 CEUS for the characterization of ovarian lesions.

Hypothesis: SI on BR55 CEUS is significantly higher for ovarian malignant versus benign lesions.

SI on BR55 CEUS will be defined as that of the target lesion of the subject; while the TS will be classified as malignant lesion if cancer is found or as benign lesion if no cancer is found. The empirical distribution of SI on BR55 CEUS will be assessed in each group (malignant and benign lesion) and, if necessary, apply a transformation to approximate normality. A t-test will be performed to test for a difference in mean signal intensity on BR55 CEUS between the malignant and benign groups. In addition, a Receiver Operating Characteristic Curve (ROC) analysis will be performed of SI on BR55 CEUS in predicting presence of a malignant lesion as determined by TS. This will be performed per subject as defined above.

Additionally, SI on BR55 CEUS will be categorized as no signal, low signal, and high signal and will be analyzed versus the TS results. Cross tabulation of the 3 SI categories versus TS will be presented and a logistic regression will be performed.

Relationship between the SI of the target lesion on BR55 CEUS and the tumor size as determined by TS

To explore if SI at BR55 CEUS is related to tumor size, SI of the target lesion will be plotted against tumor diameter as measured by TS, where tumor diameter is set to 0 for subjects without cancer. The plots will be analyzed qualitatively to determine detection limits of the technology.

Correlation between in vivo SI of the target lesion on BR55 CEUS and ex vivo VEGFR2 expression as determined by IHC

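### The plots of signal intensity against size can describe only lesions already visible before BR55, on a size axis not tied to the tissue measured, so they cannot set an unqualified detection limit

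*Combined protocol and SAP*

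**What the plan says.** The Objectives include, as an additional exploratory aim, assessing how SI of the target lesion relates to tumor size by histopathology. The matching subsection of Efficacy Analysis gives the method: "SI of the target lesion will be plotted against tumor diameter as measured by TS". It then fixes a convention for the benign group: "where tumor diameter is set to 0 for subjects without cancer". It closes with the purpose: "The plots will be analyzed qualitatively to determine detection limits of the technology". No test is planned. The subsection does not define a detected lesion, gives no SI cut-off and has no rule for reading a limit off the plot.

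Three other places decide what can appear on the plot:

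- **Inclusion Criteria:** "Has an ovarian lesion that is visible and assessable with trans-vaginal ultrasound".
- **Imaging procedure outline:** unenhanced ultrasound (UEUS) is done in every subject "to identify the target ovarian lesion (as defined in the imaging manual") and to choose the imaging plane, before BR55. The section adds: "In case of complex cystic ovarian lesions, the target lesion is defined as the solid component of the lesion itself".
- **Quantitative Assessment of BR55 Enhancement:** SI is obtained by "drawing a Region of Interest (ROI) within the target lesion to measure SI".

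On how the diameter is obtained, the plan says only: "Histopathology measurements and immunohistochemistry analysis will be described in a separate dedicated manual".

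**The concern.** A detection limit is the size below which a technique stops finding lesions. To estimate it, lesions must enter the data whether or not they can be seen by other means. Here a lesion not seen before contrast has no target, no region of interest and no point on the plot. The small end of the size axis is set by the entry rule, and a reader of the report could mistake that boundary for a property of BR55.

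The axis adds two difficulties. For complex cystic lesions the vertical axis describes the solid part, while the horizontal axis may describe something larger. For subjects without cancer the horizontal value is a constant that carries no size information. At stake is the interpretation of one exploratory objective: what the report may say about lesion size and BR55 signal.

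**Working it through.** **Plan's own figure.** There is none to reproduce. No limit, threshold or precision target is stated, and the Sample Size section says that the planned 60 subjects (about 30 malignant, 30 benign) have no statistical basis. The documents give no lesion sizes, so every size below is an assumption used for illustration.

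**1. Selection on visibility.** The entry criterion does not itself say unenhanced. That follows from the Imaging procedure outline, where UEUS identifies the target before BR55. Let v be the smallest visible size and d50 the size at which half of malignant lesions enhance. Assume:

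- 30 malignant lesions, all of diameter v or more;
- log-normal diameters with median 40 mm and log-SD 0.8, before truncation at v;
- probability of enhancement at diameter d = 1 / (1 + (d50/d)^4), that is, logistic with slope 4 on log diameter.

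Mean number of non-enhancing lesions out of 30, and chance of seeing none (4,000 simulated trials per cell):

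| d50 | v = 5 mm | v = 10 mm | v = 20 mm |
|---|---|---|---|
| 3 mm | 0.04; 96% | 0.01; 99% | 0.00; 100% |
| 10 mm | 1.82; 16% | 1.10; 33% | 0.23; 79% |
| 20 mm | 6.55; 0% | 5.70; 0% | 2.68; 6% |

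With d50 below the floor (first row), almost every trial shows only enhancing lesions and the limit cannot be found. With d50 at 20 mm, non-enhancing lesions do appear and a limit among visible lesions can be explored.

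**2. What a run of enhancing small lesions would show.** If all k of the k smallest malignant lesions enhance, the exact lower 95% limit (two-sided) on the detection probability is 0.025^(1/k):

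- k = 3: 29%
- k = 5: 48%
- k = 10: 69%
- k = 30: 88%

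**3. Axis in complex cystic lesions.** If the pathology diameter is that of the whole tumor and the solid part is a fraction f of it, a solid target of s mm is plotted at s/f. For s = 10 mm:

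- f = 0.75: 10/0.75 = 13.3 mm
- f = 0.50: 10/0.50 = 20 mm
- f = 0.25: 10/0.25 = 40 mm
- f = 1 (wholly solid): 10 mm, no shift

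**4. Diameter 0 for subjects without cancer.** The planned share is 30/60 = 50% of points. Suppose SI does not depend on size among malignant lesions, and let D be their mean diameter and Δ the malignant-minus-benign difference in mean SI. The covariance of diameter and SI over all points is then 0.5 × 0.5 × D × Δ = 0.25·D·Δ. This is positive whenever Δ is positive, which is the plan's own hypothesis in its comparison of SI with the truth standard. An upward trend would appear with no size effect at all.

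**The case against.** The strongest reply is that the stated objective is the relationship between SI and histopathological size, not a detection limit. Visibility selection does not prevent that relationship from being explored over the sizes enrolled. The study concerns characterization of lesions already found, so a limit conditional on visibility is the clinically relevant one. The plot is exploratory and has no test. All of this stands, and it is why the point is minor. It does not rescue the closing sentence, which claims a limit for the technology without that condition.

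Three stronger readings are tempting, and the documents do not support them:

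- **That no limit of any kind can be read.** The third row of the table shows otherwise: if the true limit lies above the floor, 2.7 to 6.6 of 30 malignant lesions fail to enhance on average.
- **That solid-component SI is plotted against whole-tumor diameter.** The text says only that the diameter is the one measured by the truth standard. Measurement is left to a manual that is not part of these documents and may define it for the solid component. The question also concerns complex cystic lesions only, and their share is not given.
- **That the smallest enhancing lesion will be reported as the limit.** No reading rule is stated, so this is a risk and not a plan.

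**Conclusion.** The point holds in limited form. By design there is no information below the visibility floor, whatever sizes are assumed, and any limit above it is conditional on lesions seen before contrast. For complex cystic lesions the two axes are not tied to the same object. That is an undefined axis and not a demonstrated mismatch; the 13 to 40 mm readings for a 10 mm target apply only if pathology measures the whole tumor and the solid fraction is 75% to 25%. Placing about half of the points at diameter 0 is explicit in the text and mixes the malignant-benign difference into any trend read across all points.

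Severity is minor: one additional exploratory, qualitative analysis is affected, and sensitivity, specificity and safety are not. The simulated percentages depend on the assumed size distribution and detection curve; the conclusion about the floor does not.

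**What to change.** 1. Keep the plot against histopathology diameter, because the objective specifies it, but show it for malignant lesions. State which component the diameter measures in complex cystic lesions.
2. Add a plot of SI against the size of the target that the region of interest samples: the solid component in complex cystic lesions, the lesion itself otherwise. Measure it on the UEUS images already acquired. Place benign lesions at their real size and mark them separately.
3. Replace the last sentence of the subsection with: *The plots will describe SI by size among lesions visible on unenhanced ultrasound; any apparent size limit applies only to such lesions and is not a detection limit of the technology.*

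The cost is one extra measurement per subject, a short wording change and a narrower claim. The ultrasound size is not the histopathology size named in the objective, so the second plot supplements the first and does not replace it. No visit or procedure is added.

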All patients receiving any dosage of investigational product will be included in the safety population on which safety analyses will be carried out. Summary tables, including change from pre-dose to post-dose where applicable, will be presented for the following safety endpoints:

- Adverse Events
- Clinical Laboratory Evaluations
- Vital Signs
- ECG abnormalities

All adverse events will be coded using applicable dictionaries and summarised by body system organ class and preferred term, by intensity and by causal relationship to the IMP. Only those occurrences which occur from the start of IP/IMP administration through the follow-up period defined in the protocol will be tabulated in the Clinical Trial Report as “adverse events”.

Concomitant medications will be coded according to therapeutic area using the WHO drug reference list. Concomitant medications recorded between signing of informed consent and follow-up will be presented in data listings for all subjects dosed.

Efficacy Analysis

General

Efficacy analysis will include the data from all evaluable subjects who are dosed and have efficacy data available. The results will be presented for each dose group, if applicable. Except as noted, the statistical tests will be two-sided at the 0.05 level of significance with 95% confidence limit.

Differentiation between malignant and benign ovarian lesions - visual score vs. histopathology as the (TS)

The objective of this study is to determine the ability of BR55 CEUS to differentiate between malignant and benign ovarian lesions in subjects with suspected ovarian cancer on the basis of a visual score (semi quantitative visual assessment of BR55 enhancement) using histopathology as the TS.

Contrast-enhanced US images of the ovaries will be assessed by the investigator as 3-point scale for contrast enhancement of BR55. Frequency tables will be provided for enhancement scores (none, weak enhancement, and strong enhancement) by histology assessment results (malignant and benign). The primary analysis will be performed based on the assumption that benign lesions will not show VEGFR2 expression and therefore will not present stationary enhancement at BR55 CEUS.

The primary variables for the characterization are sensitivity and specificity in differentiation of target ovary lesions. The following parameters will be calculated and the 2-sided 95% confidence intervals for the sensitivity and specificity will be estimated.

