Hypothesis: There is a significant relationship between *in vivo* SI of the target lesion on BR55 CEUS and *ex vivo* VEGFR2 expression level, as measured by the angiogenesis score. A two-sample t-test will be performed to test for a relationship between angiogenesis score and *in vivo* SI of the target lesion on BR55 CEUS.

Correlation between SI of the target lesion on BR55 CEUS vs. microvessel density
(MVD)

Hypothesis: SI of the target lesion on BR55 CEUS significantly correlates with *ex vivo* MVD. The correlation coefficient between the subject's target lesion SI and MVD will be estimated and the null hypothesis that correlation coefficient is zero will be tested.

Sample Size

This is an exploratory study. The sample size determination is not based on the statistical considerations and assumptions. About 60 female subjects (approximately 30 subjects with a malignant lesion and 30 with a benign lesion) will be prospectively enrolled.

Data Handling

All data collected will be entered into the database and displayed in the subject data listings. In general, no imputation algorithms will be used to estimate missing safety and efficacy data, and tables will display counts of missing values.

Interim Analyses

No interim analysis is planned.

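### The SI–VEGFR2 and SI–MVD tests take no account of lesion type, so a significant result need not show that SI follows the marker among malignant lesions; add one pre-specified within-malignant estimate per marker

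*Combined protocol and SAP*

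**What the plan says.** All references are to the combined protocol and SAP.

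- **SI and VEGFR2.** The hypothesis in the VEGFR2 correlation section concerns "VEGFR2 expression level, as measured by the angiogenesis score". The method is: "A two-sample t-test will be performed to test for a relationship between angiogenesis score and" SI of the target lesion.
- **SI and MVD.** The next section estimates one correlation coefficient across subjects, and "the null hypothesis that correlation coefficient is zero will be tested".
- **Who is analysed.** Efficacy Analysis, General: "Efficacy analysis will include the data from all evaluable subjects who are dosed and have efficacy data available". The only split named there is by dose: "The results will be presented for each dose group, if applicable". No section restricts, stratifies or adjusts the two marker analyses by lesion type.
- **What the plan expects by lesion type.** The section comparing SI with the truth standard hypothesises that "SI on BR55 CEUS is significantly higher for ovarian malignant versus benign lesions". The primary analysis assumes that "benign lesions will not show VEGFR2 expression and therefore will not present stationary enhancement at BR55 CEUS".
- **Design.** Sample Size plans about 60 subjects, roughly 30 with each lesion type, and says the number has no statistical derivation. Objectives lists the VEGFR2 and MVD correlations as exploratory, separately from the comparison of SI between malignant and benign lesions.

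**The concern.** SI is a continuous measurement, obtained by "drawing a Region of Interest (ROI) within the target lesion to measure SI". The VEGFR2 hypothesis is about level of expression, which suggests a graded relationship. The sample, however, is a mixture of two lesion types, and by the plan's own expectations both SI and VEGFR2 differ between them. A mixture of that kind produces an association across all subjects even if SI and the marker are unrelated inside each type.

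What is at stake is what the exploratory result can be said to mean. The plan already has a t-test and an ROC analysis of SI by lesion type. If the marker analyses only restate that contrast, they add nothing to it, and nothing planned would show a reader of the summary tables which of the two has happened. The primary sensitivity and specificity are not touched.

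**Working it through.** **Inputs from the documents.** Two-sided 0.05 (Efficacy Analysis, General); about 30 malignant and 30 benign lesions (Sample Size). No power, target correlation or group difference is stated for any marker analysis, so there is no figure of the plan to reproduce beyond 30 + 30 = 60.

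**Assumptions.** Let d be the malignant–benign difference in within-type SDs. The documents give no value, so a range is used. Data are normal and the within-type correlation is zero unless stated. Rejection rates come from 20,000 simulated trials per scenario.

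**1. Correlation produced by lesion type alone.** For a 50:50 mixture with the same d in SI and marker,

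r = (d/2)² / [1 + (d/2)²].

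At d = 1.0: 0.25 / 1.25 = 0.20. At d = 1.5: 0.5625 / 1.5625 = 0.36. With 60 subjects, an observed |r| above 0.254 is significant.

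**2. How often the all-subject correlation test rejects.**

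| d in both SI and MVD | r from type alone | 30/30 | 20/40 or 40/20 |
|---|---|---|---|
| 0.5 | 0.06 | 7% | 7% |
| 0.8 | 0.14 | 18% | 16% |
| 1.0 | 0.20 | 34% | 29% |
| 1.5 | 0.36 | 85% | 78% |
| 2.0 | 0.50 | >99% | 99% |

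The effect needs a type difference in both variables. With SI d = 1.5, the rejection rate is 5% if MVD does not differ by type, 20% if MVD d = 0.5, and 57% if MVD d = 1.0.

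**3. The VEGFR2 t-test.** The synopsis does not define its two groups. Assume, for illustration, that it compares SI in VEGFR2-positive and VEGFR2-negative lesions, that all benign lesions are negative (the plan's assumption), and that SI is unrelated to VEGFR2 among malignant lesions. At SI d = 1.0:

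| Malignant lesions VEGFR2-positive | Test rejects |
|---|---|
| 50% | 54% |
| 70% | 76% |
| 90% | 93% |
| 100% | 97% |

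At 100% the two groups are the malignant and benign lesions, and the test is the SI t-test already planned against the truth standard.

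**4. Estimates that separate the two explanations.** Under the same zero within-type correlation, the within-malignant Spearman test and the type-adjusted Spearman test each reject in about 5 to 6% of trials, whatever the value of d. Two cautions follow:

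- If a claim may rest on any one of the within-malignant, within-benign and adjusted tests, at least one is significant in about 11–12% of trials. A single estimate should therefore be named.
- If SI and marker both sit at floor in 90–100% of benign lesions, the adjusted test rejects in about 8–17% of trials. The plan expects benign lesions near floor, so the adjusted estimate is not a safe basis for a claim.

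**5. Precision of the within-malignant estimate.** By Fisher z, a Pearson correlation is detectable with 80% power at tanh(2.80/√27) = 0.49 with n = 30, and at tanh(2.80/√17) = 0.59 with n = 20. Spearman needs a little more. Its simulated power is about 75% at 0.49 (n = 30) and 74% at 0.59 (n = 20), and about 0.51 is needed for 80% with n = 30. An observed Spearman of 0.50 with n = 30 has a 95% CI of tanh(0.549 ± 1.96 × √(1.06/27)), about 0.16 to 0.73.

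**The case against.** The strongest reply is that no planned analysis is wrong. The objective is the correlation between SI and marker, and the plan tests that. It never promises a relationship beyond lesion type. This stands. A reader might infer that the tests have an inflated type I error or that a significant result would be spurious, and the documents support neither. The null hypothesis of no overall association is properly tested. For VEGFR2 the between-type contrast may also be part of the real relationship, because the plan makes VEGFR2 expression the reason that malignant lesions enhance.

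Three further points stand in part.

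- **MVD.** No section says that MVD differs by lesion type. If it does not, the rejection rate stays at 5% and there is nothing to correct. A reader should not infer that the MVD result is bound to be affected.
- **Undefined t-test groups.** The groups may be set out in the separate histopathology and immunohistochemistry manual, so their absence here is not claimed as a fault. The VEGFR2 percentages above depend on the assumed positive/negative grouping.
- **Inclusion of benign lesions.** That all 60 subjects enter the marker analyses is the natural reading of the efficacy section, but it is not stated outright. The analyses are limited to evaluable subjects with data, and the immunohistochemistry detail lies in the manual.

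It can also be said that the subject listings would let anyone set lesion type, SI and marker side by side. No data are lost, but a listing is not a pre-specified estimate and does not constrain what is claimed.

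**Conclusion.** The point holds as a limit on interpretation. For VEGFR2, the plan's own expectations allow a significant all-subject result to arise from the malignant–benign difference alone, so such a result need not show that SI follows expression level among malignant lesions. For MVD the same is true only on the condition, not stated in the documents, that MVD also differs by lesion type.

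The size depends on assumed group differences. Modest ones (0.5 SD in both variables) barely move the correlation test from 5%, while differences of 1.5 SD or more make a significant result likely without any within-type relationship. The point rests on benign lesions being included in the marker analyses. It concerns exploratory objectives only and is an optional, cheap improvement.

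**What to change.** Keep the all-subject analyses as planned. Before results are seen, add for each marker:

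1. One pre-specified estimate: the Spearman correlation between SI and the marker within malignant lesions, with 95% CI.
2. A scatter plot of SI against the marker, marked by lesion type.
3. A sentence stating that any conclusion that SI follows the marker beyond lesion type rests on estimate 1 alone.

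Within-benign and lesion-type-adjusted correlations may be shown as descriptive results. Omit the adjusted one when most benign values of both SI and marker are at floor.

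The cost is one short table and one plot per marker, from data already collected, with no change to sample size or conduct. The drawback is low precision. Discontinued subjects are not replaced and the split is only approximate, so fewer than 30 malignant lesions may be available. The report should say that a non-significant within-malignant result does not show absence of a relationship.
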